## 3. Hypotheses

[figure not shown]
- a) Adjuvant melatonin will reduce the incidence of lung cancer recurrence of NSCLC two years after surgical resection.
- b) Adjuvant melatonin will reduce disease specific 2-year mortality following lung cancer resection.
- c) Melatonin will lead to a reduction in chemotherapy related toxicities and have no impact on adverse effects due to radiation therapy.
- d) Melatonin will lead to improved QOL, less fatigue, improved sleep, and have no impact on depression or anxiety in patients following lung cancer resection.

## NSCLC Adjuvant melatonin RCT

- e) Melatonin will increase NK cell activity of people who are ingesting this at a dose of 20mg daily.
- f) Melatonin will create a decrease in both inflammatory and anti-inflammatory cytokines including: IL4, IL6, IL10, IL12, IL15, IFN- $\alpha$ , GM-CSF, TNF- $\alpha$ , IFN- $\alpha$ , TGF- $\beta$ 1, and VEGF in people who are ingesting melatonin at a dose of 20 mg daily.

## 4. Study Design

The study is a two-arm, randomized, placebo-controlled, blinded trial among 640 subjects who have been diagnosed with NSCLC and are scheduled for surgical resection. Of these 640 patients 80 patients at the Ottawa Hospital will be included in the biomarker sub-study. Patients will be recruited into the main trial at the Ottawa Hospital as well as other centers across Canada.

**NOTE: Past the two year follow up (until a maximum of five years), patients will be followed for recurrence date and/or date of death (using medical records, patient follow-up, and family follow-up). No questionnaires will be given past the 2-year follow up.**

## 5. Eligibility Criteria

### 5.1 Inclusion Criteria

1. Adult males or females with a clinical diagnosis confirmed by pathology of Stage I, II, III, or IV primary NSCLC who are eligible and scheduled for surgical resection.
2. Willingness to adhere to randomized treatment.
3. Availability for follow-up schedule of visits.
4. Ability to answer self- and interviewer- administered questions in English or French, or have an appropriate person available to assist with translation.

5. Understand and sign a written informed consent form in English or French, or have an appropriate person available to assist with translation.
6. For the sub-study only, willingness to have additional blood taken for study purposes.
7. Verbal confirmation from females of childbearing age that they are not pregnant, or documented birth control method or menopause. Breastfeeding patients will not be included in this trial.

## **5.2 Exclusion criteria**

1. Taking exogenous melatonin for reasons related or unrelated to the diagnosis of lung cancer.
2. Synchronous lesions, or any situation where all cancer cannot be resected.
3. Pregnant and breastfeeding patients will not be included in the trial. A verbal confirmation that patients are not pregnant or breastfeeding has been deemed sufficient as the chance that patients from this population are either pregnant or breastfeeding is exceptionally low.

# **6. Site, Protocol, Methods and Procedures**

## **6.1 Primary Site**

The Ottawa Hospital is the Institution lead in this clinical trial. At this location, a multidisciplinary team will be responsible for the coordination of all the activities related to this study. The Ottawa Hospital is the only site involved in recruiting the additional 80 patients for the sub-study.

## **6.2 Participant Institutions**

Centres wishing to participate in this trial are required to obtain full board local ethics approval of the protocol and consent form by the appropriate Research Ethics Board prior to study commencement. Centers are also required to submit any subsequent amendments to their Research Ethics Board and provide the coordinating center with approval letters. Any centre joining this trial must sign a Clinical Trial Agreement before trial commencement at their site. As per Good Clinical Practice guidelines, an annual renewal of the study is required by the participating center's research ethics board (unless otherwise specified).

## **6.3 Recruitment and screening**

Patients will be identified and selected prospectively from investigators' patient records. Entry into the trial may occur pre- or post-operatively, up to the point at which the trial intervention begins on the day of discharge from hospital up to 60 days after surgery. Even though there is a recruitment window of 60 days, it is important to enroll patients as soon as possible after surgery. Recruitment and patient accrual will occur during the first five years of the trial. To facilitate the enrollment REB approved informative brochures about the study may be placed in appropriate locations (i.e., exam rooms and waiting rooms). Recruitment for the 80 patients in the sub-study will be done post-operatively, as they will need to have a baseline blood draw at their first post-operative appointment.

The trial began enrollment in Oct 2007, and we have currently have eight sites including the Ottawa Hospital actively recruiting patients. Dissemination of the trial results will take place through publication in a high impact journal, through conference presentations, and to lung cancer patients via outreach to patient advocate groups and societies.

In all presentations of the phase III trial, the funding contributions of the Lotte and John Hecht Memorial Foundation and the Gateway for Cancer Research will be acknowledged. In all presentations of the phase II substudy, Gateway's sole contribution and support will be acknowledged.

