#### **6.4 Interventions**

Patients who appear to meet eligibility criteria will be approached and asked to consent to the trial by the research coordinator. After eligibility criteria have been confirmed by the investigator or medically qualified delegate patients will be randomized using a centralized system at The Ottawa Hospital to either active melatonin group or placebo. Randomization will be stratified according to cancer staging (I/II vs. III/IV). Allocation bias will be prevented by using a randomization table with variable blocks of 4 and 6. Only the Pharmacy Research Technician at the Ottawa Hospital can see the randomization table and treatment assignments.

Patients, physicians, and the research coordinator will be kept strictly blinded as to individual group allocation and treatment. The intervention, active or placebo, will be given to participants in opaque bottles with the patient study code clearly written on the corresponding container. The clinical trial pharmacist at the coordinating site will be responsible for the coding and container labeling of all containers. Instructions for taking the intervention will be identical for both control and melatonin groups. The research coordinator will be responsible for the dispensing of the pills (both active and placebo).

Melatonin or placebo will be provided to patients either on the day of discharge or up to 60 days post-operative from the hospital. In the phase II substudy, participants will only be given the intervention four weeks following surgery. This wait period is to reduce the confounding effect of the surgery on the surrogate measures we are testing. Patients will be responsible for taking their doses and will be required to report any missed doses to the research coordinator. To ensure optimal compliance, the research coordinator will telephone each patient once a week for two weeks at the beginning of the trial. Telephone calls will then be made as needed until the completion of one year while the patient is on the study drug.

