Patients' medical records will be reviewed in order to record cancer recurrence or death. Should the information not be available in the medical records, their records will be requested from the Canadian Cancer Registry. If patient information cannot be found in the registry, surgeons will be asked to follow up with the patient's GP in order to find out whether they had a recurrence or died. If the patient's GP does not have this information, but directs us elsewhere, or if the medical records indicate that the patient was discharged to another facility (eg: another hospital), this facility will be contacted. At the facility's request, the signed patient consent form will be provided in order for them to release the information on the patient's death or recurrence. If this information cannot be retrieved through searching patient records in any of the above methods, patients will be contacted directly. Patient contact will begin with a letter and brief questionnaire to the last known address (letter and questionnaire provided by the coordinating centre) requesting an update on patient health status. If the patient does not respond to the letter, the study coordinator will contact the patient at their last known telephone number, and ask for a health status update. If the patient cannot be contacted, and all other options are exhausted, the study coordinator will contact the patient's next of kin (telephone script provided by the coordinating centre). Should we be unable to follow up in any of the above methods, participants

will then be considered lost to follow up. Sites should ensure that the letter, questionnaire, and telephone script receive REB approval prior to use.

Patients who 1) withdrew from the trial before starting the intervention, or 2) were enrolled but considered to be screen fails (did not meet inclusion criteria) and did not start the intervention, or 3) recurred within the first two years, will be followed only for outcome data (recurrence and/or mortality). The “Follow-up for Withdrawals and Screen Fails (who did not start intervention)” CRF will be completed annually for these patients (up to 5 years post-op). Adverse events will not be tracked for these patients.

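### Randomisation is not held until after surgery, so patients can be allocated before complete resection and pathology are known, and those who never start treatment have no defined outcome window

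*Combined protocol and SAP*

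**What the plan says.** Section 6.3 sets the time of entry: "Entry into the trial may occur pre- or post-operatively, up to the point at which the trial intervention begins". Only the 80 biomarker sub-study patients must be recruited after the operation.

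Section 6.4 sets the trigger for allocation: "After eligibility criteria have been confirmed by the investigator or medically qualified delegate patients will be randomized using a centralized system". It gives no timing relative to surgery or the pathology report. Stratification is by stage I/II against III/IV, without saying whether clinical or pathological stage is meant. On dispensing, the same section says: "Melatonin or placebo will be provided to patients either on the day of discharge or up to 60 days post-operative from the hospital".

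Eligibility looks both ways. Inclusion criterion 1 requires "Adult males or females with a clinical diagnosis confirmed by pathology of Stage I, II, III, or IV primary NSCLC", in patients "who are eligible and scheduled for surgical resection". Exclusion criterion 2 removes "Synchronous lesions, or any situation where all cancer cannot be resected".

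Section 6.6 provides outcome-only follow-up for patients who withdrew before starting, and for those who "were enrolled but considered to be screen fails (did not meet inclusion criteria) and did not start the intervention". Section 8 analyses patients in the group to which they were randomised. Section 6.5 counts the two years of the primary outcome from the start of the intervention.

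**The concern.** Treatment cannot begin before discharge, yet the text lets allocation happen before the operation. Between the two, a patient may prove not fully resectable, may not have NSCLC on pathology, may die around surgery, or may withdraw. Each such patient, once randomised, belongs to the intention-to-treat population but never takes a capsule.

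Two consequences follow for the primary analysis. Never-starters have no date from which to count two years, so the analyst must either drop randomised patients or improvise a start date. They also contribute outcomes that melatonin could not have altered, which pulls the arms together.

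A lesser consequence concerns the only stratification factor. A patient allocated before surgery can be stratified only on pre-operative stage. One allocated afterwards could be stratified on pathological stage, and the text does not say which is to be used.

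**Working it through.** **Timing, from the text.** Entry may be before surgery (6.3). Inclusion criterion 1 can be met by a patient still awaiting surgery (5.1). Allocation follows confirmation of eligibility (6.4). Capsules start between discharge and day 60 (6.4). No sentence requires the operation or the pathology report to come before allocation in the main trial. Allocation before surgery is therefore permitted, though nowhere prescribed.

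**Start of the outcome window.** Section 8 keeps every randomised patient; section 6.5 starts the clock at commencement of the intervention. For a randomised never-starter that date does not exist. Other sections use different clocks: 6.6 follows never-starters up to five years after the operation, and 6.12 follows those who stop the drug up to five years after enrolment. None supplies a start date for the two-year outcome.

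**The plan's own power figure.** Section 7.0 claims 80 to 90% power with 320 per arm, a reference rate of 5% and a difference of 6 to 7 points. Alpha is not stated; I assume two-sided 0.05.

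Power = Φ{[Δ − 1.96·√(2p̄(1−p̄)/n)] / √[(p1(1−p1) + p2(1−p2))/n]}

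- 5% v 11%: 0.80
- 5% v 12%: 0.89

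The claim reproduces.

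**Dilution.** Let x be the share of all randomised patients who never start, c and t the event rates with placebo and melatonin among starters, and r the event rate in never-starters, equal in both arms.

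- Control arm: (1−x)c + xr
- Melatonin arm: (1−x)t + xr
- Difference: (1−x)(c−t), whatever the value of r
- Approximate equivalent sample size: 640(1−x)²

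The documents do not give x, so I assume 5%, 10% and 15%. The 5-point difference is the 20% v 15% case of section 7.0. The last column takes 12% v 5%, 320 per arm and r = c.

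| x | 5-point difference becomes | Equivalent N | Power, 12% v 5% |
|---|---|---|---|
| 0 | 5.00 | 640 | 0.89 |
| 5% | 5 × 0.95 = 4.75 | 640 × 0.9025 = 578 | 0.85 |
| 10% | 5 × 0.90 = 4.50 | 640 × 0.81 = 518 | 0.80 |
| 15% | 5 × 0.85 = 4.25 | 640 × 0.7225 = 462 | 0.75 |

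Dropping never-starters after randomisation, at the same shares, would leave 304, 288 or 272 per arm and power of 0.87, 0.86 or 0.84, at the cost of abandoning intention to treat.

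**How much early allocation could contribute.** The 80 sub-study patients enter after surgery, so at most 640 − 80 = 560 could be allocated before it. An overall 5% is 32 patients. For early allocation alone to produce that, 32/560 = 5.7% of those patients would have to never start, even if all 560 were allocated before surgery. For 10% and 15% overall the figures are 64/560 = 11.4% and 96/560 = 17.1%.

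**The case against.** The strongest reply is that the protocol already prevents the problem. Section 6.4 randomises only after eligibility is confirmed. If complete resection and pathological NSCLC are part of eligibility and are settled only by surgery, eligibility cannot be confirmed beforehand. Section 6.3 also urges enrolment soon after surgery. A careful site could read it that way, but the text does not say so, and inclusion criterion 1 describes a patient whose operation is still scheduled. The trial has eight recruiting sites, and they could differ.

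Other parts of the objection stand. A reader might infer more than the documents support:

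- *That patients are in fact randomised before surgery.* Section 6.6 says enrolled, not randomised, so it makes this plausible but does not prove it. Screen failures who started capsules (6.9) received them after surgery and say nothing about when they were allocated.
- *That restaging at surgery affects eligibility.* Stages I to IV all qualify, so restaging can change only the stratum.
- *That post-operative entrants are stratified on pathological stage.* The text specifies neither kind of stage.
- *That a mixed stratum biases the result.* It does not. Allocation is still random within strata, the primary test is an unadjusted chi-square, and the planned logistic regression could use pathological stage.
- *That near-certain events in unresected patients shrink the absolute difference further.* By the formula above they do not. They raise the variance and move the relative risk towards 1. With an assumed 80% event rate and no treatment effect in 5% or 10% of patients, power for 12% v 5% is 0.73 or 0.59.

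Patients allocated after surgery can also withdraw before the first capsule, so later allocation reduces never-starters without eliminating them. Early allocation may also have a practical use, since bottles are coded for each patient at the coordinating site.

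**Conclusion.** The point holds as a statement of what the protocol permits. Allocation may precede knowledge of complete resection and pathology, and a randomised patient who never starts is kept in the primary analysis without a start date for the outcome. The second part follows directly from sections 6.5 and 8 and needs no assumption about frequency.

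The size of the dilution is conditional. With 5% to 15% of all randomised patients never starting, a 5-point difference falls to between 4.75 and 4.25 points, equivalent to about 578 down to 462 of 640 patients. Those shares are assumed, are not confined to pre-operative entrants, and take event rates in never-starters to be equal between arms.

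This is a loss of efficiency and a gap in the outcome definition. The comparison between arms remains unbiased provided never-starters are kept and counted from a common date. A larger and separate problem is that the 20% v 15% scenario has power of about 0.38 with no dilution at all, against the nearly 90% claimed in section 7.0.

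**What to change.** In sections 6.3 and 6.4, allow consent before or after surgery, but randomise only after resection, when complete resection and NSCLC are confirmed and the site is ready to dispense, within the existing 60-day window. State that the stratum uses pathological stage. Patients who consented before surgery and fail at operation are then screen failures who were never randomised.

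In sections 6.5 and 8, state that patients already randomised who never start remain in the intention-to-treat analysis, and count the two years from a date defined for all patients, such as randomisation or surgery, fixed before unblinding. Randomisation is the one date that every randomised patient has; a surgery date would be missing if an operation were cancelled.

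The cost is protocol wording and one change to the central randomisation step. Some discharge-day starts may have to wait for pathology, or need coded bottles held at the site. The change in timing helps only patients not yet randomised. Enrolment began in October 2007, the latest listed amendment is dated December 2014 and recruitment was expected to end in January 2015, so at that stage the analysis rule carries most of the benefit.

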#### **6.4 Interventions**

Patients who appear to meet eligibility criteria will be approached and asked to consent to the trial by the research coordinator. After eligibility criteria have been confirmed by the investigator or medically qualified delegate patients will be randomized using a centralized system at The Ottawa Hospital to either active melatonin group or placebo. Randomization will be stratified according to cancer staging (I/II vs. III/IV). Allocation bias will be prevented by using a randomization table with variable blocks of 4 and 6. Only the Pharmacy Research Technician at the Ottawa Hospital can see the randomization table and treatment assignments.

Patients, physicians, and the research coordinator will be kept strictly blinded as to individual group allocation and treatment. The intervention, active or placebo, will be given to participants in opaque bottles with the patient study code clearly written on the corresponding container. The clinical trial pharmacist at the coordinating site will be responsible for the coding and container labeling of all containers. Instructions for taking the intervention will be identical for both control and melatonin groups. The research coordinator will be responsible for the dispensing of the pills (both active and placebo).

Melatonin or placebo will be provided to patients either on the day of discharge or up to 60 days post-operative from the hospital. In the phase II substudy, participants will only be given the intervention four weeks following surgery. This wait period is to reduce the confounding effect of the surgery on the surrogate measures we are testing. Patients will be responsible for taking their doses and will be required to report any missed doses to the research coordinator. To ensure optimal compliance, the research coordinator will telephone each patient once a week for two weeks at the beginning of the trial. Telephone calls will then be made as needed until the completion of one year while the patient is on the study drug.

The intervention for those randomized to the melatonin group will involve the ingestion of 20 mg of melatonin taken as a single capsule nightly approximately one hour prior to bedtime. Melatonin has a soporific effect and thus nighttime administration is recommended [75]. The choice of 20 mg nightly is based on efficacy demonstrated using this dose in prior clinical research [18]. The Ontario based company, Promising Health Inc., will supply melatonin in the form of 20 mg capsules. Regulatory approval for the trial was given by the Natural Health Products Directorate (NHPD). In addition to confirming ethics approval, Health Canada's regulatory process requires strict approval regarding the chemistry and manufacturing of any NHP used in a clinical trial. Consumption of the melatonin will continue nightly for the first year of the trial.

The intervention for those randomized to the control group will receive an identical looking capsule in identical looking containers. Promising Health Inc. will also be providing the

placebo. Similar requirements for quality control and quality assurance will be required for the placebo as required for the melatonin.

## **6.5 Outcome Measures**

The primary outcome is a composite outcome including either cancer recurrence and/or mortality within two years following the commencement of the intervention. Recurrence will be determined by clinical examination by the patient's thoracic surgeon in addition to radiological evidence of loco-regional or systemic recurrence of lung cancer. While contrast enhanced chest CT scan at one and two years post resection is the preferred radiological assessment, the standard of care radiological assessments for each site is acceptable. For study purposes, only chest CT is requested at 1 and 2 years, but results of head and abdominal CTs will be recorded if applicable. As per standard of care, lateral and P/A chest radiographs will be assessed at 3 weeks and at 3, 6, 9, 12, 18 and 24 months following hospital discharge.

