## 2. Study Objectives

### 2.1 Primary Objectives

1. To determine the effectiveness of adjuvant melatonin as compared to placebo in the prevention of cancer recurrence and mortality two years after surgical resection of NSCLC.
2. To explore the effect of melatonin on promising biological markers within participants enrolled in the larger clinical trial. These markers include the most promising assays that address areas in which melatonin may act against cancer. The assays include NK cell function and cytokine levels. In addition to addressing the very important issue of mechanism of action, the additional 80 participants will further contribute to the power of the phase III trial.

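### Section 6.5 starts the two-year primary outcome at capsule start, Sections 2.1 and 3 at resection; taken literally, 6.5 leaves randomised non-starters without a window

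*Combined protocol and SAP*

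**What the plan says.** Section 6.5 (Outcome Measures) sets the endpoint: "The primary outcome is a composite outcome including either cancer recurrence and/or mortality within two years following the commencement of the intervention". I read commencement of the intervention as the first capsule.

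Other sections use a different clock:

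- Section 2.1, the primary objective, refers to "prevention of cancer recurrence and mortality two years after surgical resection of NSCLC".
- Section 3, hypothesis a: "Adjuvant melatonin will reduce the incidence of lung cancer recurrence of NSCLC two years after surgical resection". Hypothesis b: "Adjuvant melatonin will reduce disease specific 2-year mortality following lung cancer resection".
- Section 6.5 itself times the scan from surgery: "contrast enhanced chest CT scan at one and two years post resection is the preferred radiological assessment".

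The interval between the two clocks varies by patient. Section 6.4 states: "Melatonin or placebo will be provided to patients either on the day of discharge or up to 60 days post-operative from the hospital". In the substudy, "participants will only be given the intervention four weeks following surgery". Section 6.3 allows entry before or after the operation.

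On who is followed and analysed, Section 6.6 provides for patients who "withdrew from the trial before starting the intervention", and for screen failures who never started. Both groups are followed annually for recurrence and death, for up to five years after the operation. Section 8 analyses patients in the group to which they were randomised and uses an unadjusted chi-square test on event proportions. Section 6.12 asks patients who stop capsules early whether they agree to continued follow-up. The tracing steps in Section 6.6 are introduced for follow-up past two years and end by classing untraceable patients as lost. No section says how an unknown two-year status enters the primary test.

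**The concern.** An intention-to-treat comparison needs a time zero that every randomised patient has. First capsule is not one, because a patient who never starts has no such date. For a patient who does start, a recurrence or death after randomisation but before the first capsule falls outside the window as written. The Section 6.5 window also closes later than the preferred two-year CT, by however long capsules were delayed.

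At stake is whether the rule is fixed in advance. With two clocks in the text, the choice of which patients and events count could be made after the results are known. One of the two readings would not give the as-randomised result that Section 8 promises. The chi-square has a related weakness: it needs a yes or no at two years for each patient and cannot use the partial follow-up of someone lost earlier.

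**Working it through.** **Inputs.** Section 7.0 gives 640 patients, 320 per arm, a 5% reference event rate, and 20% as also possible. It expects about 16 events in a substudy with 40 patients per group. Read as 16/40 this is 40%; read as 16/80 it is 20%. I use 5%, 20% and 40%. The start delay is up to 60 days, or 28 days in the substudy (Section 6.4). The plan gives no figure for the effect of the clock.

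**Clock.** Assume a constant hazard, with p the risk over two years (730.5 days). Then risk(d) = 1 − (1 − p)^(d/730.5). Moving the end of the window by 60 days gives d = 790.5, and by 28 days d = 758.5. The expected number with an event in a gap of g days is 640 × risk(g). For example, at p = 20%, 1 − 0.8^(790.5/730.5) = 21.5%, and 640 × (1 − 0.8^(60/730.5)) = 11.6.

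| Two-year risk | 28-day shift | 60-day shift | Pre-capsule events of 640, 28-day gap | 60-day gap |
|---|---|---|---|---|
| 5% | 5.2% | 5.4% | 1.3 | 2.7 |
| 20% | 20.7% | 21.5% | 5.5 | 11.6 |
| 40% | 41.2% | 42.5% | 12.4 | 26.3 |

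The gap columns suppose that everyone is randomised at surgery and starts on the same late day. Only events that also follow randomisation matter for intention to treat. With a 7-day gap from randomisation to first capsule the counts are 0.3, 1.4 and 3.1. The documents do not give the distribution of these gaps.

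**The reverse distortion.** A resection clock has its own cost. If everyone were randomised on day 60, the first 60 days could contain no countable event, so d = 670.5. The three risks would then read 4.6%, 18.5% and 37.4%.

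**Unknown status.** Section 7.0 states 80% to 90% power for differences of 6 to 7 points from 5%. A pooled two-sided 5% test (level assumed) with 320 per arm gives 80.0% for 5% v 11% and 89.0% for 5% v 12%, which agrees. Loss rates are my assumption, as the documents give none. With 10% unknown per arm at 5% v 12%:

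- Unknowns dropped (288 per arm): power 85.6%.
- Unknowns counted as event-free (4.5% v 10.8%): 85.2%.
- Unknowns counted as events (0.05 × 0.9 + 0.10 = 14.5%; 0.12 × 0.9 + 0.10 = 20.8%): 55.2%.

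As an outer bound, take Section 7.0's 20% v 15% case with 5% unknown per arm (16 of 320). Assigning all unknowns as events in one arm and event-free in the other gives 5 × 0.95 ± 5, a difference between −0.25 and 9.75 points.

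**The case against.** The strongest reply is that Section 6.5 defines an endpoint window, while the analysis set is defined in Section 8. Sections 6.6 and 8 together show that non-starters are meant to be followed and counted. That stands. A reader might infer that the plan drops non-starters from the primary analysis or fails to collect their outcomes. The documents do not support either reading. What is missing is a start date for these patients' two years, and neither section supplies one.

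A reader might also infer a biased treatment effect. The documents do not support that: the arms are blinded and share one start rule, so the clock effect should be similar in both.

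The gap counts are high-side illustrations. Section 6.3 urges early enrolment, Section 5.2 excludes disease that cannot be fully resected, and the first scheduled radiograph is three weeks after discharge. A constant hazard from surgery may therefore overstate early events. At the plan's own 5% rate the 60-day figure is under three patients. This also stands, and it is why the point is one of definition.

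For patients randomised after surgery, the Section 6.5 clock lies closer to randomisation than a resection clock does. That is correct, and it argues for considering randomisation as the origin.

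On losses, Section 6.9 says that patients who started capsules and then withdrew continue to be followed radiographically, and Section 6.12 expects withdrawal to be a minor problem. Losses may indeed be few. But Section 6.12 makes continued follow-up depend on the patient's agreement, and the chi-square cannot use incomplete follow-up at any loss rate. The extreme-case bound would apply to any trial with the same share unknown; it shows why sensitivity analyses are needed and does not predict bias.

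**Conclusion.** The conflict is real and should be corrected. Sections 2.1 and 3 and the CT schedule count from resection, while Section 6.5 counts from capsule start. Read literally, the latter does not fit the as-randomised analysis in Section 8.

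The numerical effect of the clock is modest: 0.4, 1.5 or 2.5 percentage points for a full 60-day shift at risks of 5%, 20% or 40%, and less for shorter delays. These figures rest on a constant hazard and on every patient having the longest delay. The case for change is that the rule must be single and fixed, since no large bias can be shown.

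Handling of unknown status could matter more, depending on loss rates that the documents do not give.

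Hypothesis b speaks of disease-specific mortality where Section 6.5 says mortality. Hypothesis b may be a separate mortality hypothesis, so this is a secondary wording point. The two should be reconciled so that it is clear whether a non-cancer death counts in the composite.

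**What to change.** **One time origin** for every randomised patient, whether or not capsules were started, in Sections 2, 3, 6.5 and 6.6. Two choices are workable:

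- *Randomisation*, with one fixed horizon for all, long enough to include the two-year post-resection CT. Two years already suffices for anyone randomised after surgery; for those randomised before it, the horizon must also cover the wait for the operation. Nothing after the horizon counts. The cost is a horizon slightly longer than two years.
- *Resection*, which needs the fewest text changes. It requires a stated fallback date for anyone randomised before surgery and never resected, and an acknowledgement that time before randomisation cannot contribute events.

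**Primary comparison.** Replace the unadjusted chi-square with a comparison of Kaplan-Meier event proportions at that horizon, stratified by the randomisation stratum (stage I/II v III/IV), with lost patients censored at last contact. Under the resection clock, patients randomised after surgery enter the risk set at randomisation. Add extreme-case sensitivity analyses that assign unknowns as events in one arm and event-free in the other, and the reverse. Section 8's relative risk, absolute difference and number needed to treat can be taken from the same proportions.

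**Cost.** This needs amendment and analysis-plan wording. Stage is already a stratification factor, and Sections 2.2 and 4 already call for times or dates of recurrence and death. A last-contact date may have to be added to the case report form and, with enrolment open since 2007, collected retrospectively. Kaplan-Meier assumes non-informative censoring, which the extreme-case analyses probe. With late entry, its early estimates can be unstable if few patients are at risk.
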